
Justification

We wish to demonstrate that the use of with autologous MSCs is effective as a treatment option for knee OA grades, II and III. In a large number of cases it is possible to improve the pain, function and quality of life of patients without the side effects of conventional treatments. In other cases, avoid progression to more severe stages that require joint replacement surgery. This research aims at contributing with a low-cost regenerative technique in order to change the course of the disease and significantly reduce public and private sector expenses generated by conservative and surgical OA treatments.

Main goals

- a. The aim of the present study will be to compare three types of intra-articular injections of MSC populations obtained from two clinically relevant sources: injections containing BM-MSC or AD-MSC or a combination of both of them BM-MSC and AD-MSC, in a randomized non blind clinical trial.
- b. To assess the efficacy and safety of treatment with containing BM-MSC or AD-MSC or a combination of both of them BM-MSC and AD-MSC, in relation to pain, function and quality of life in patients with knee OA.

Hypothesis Testing

H1: The combined use of BM-MSC and AD-MSC is superior for pain management in knee OA, than the use of BMSC or AD-MSC alone.

H0: The combined use of MSC from bone marrow and adipose tissue is not superior to the use of MSC derived solely from bone marrow or solely from adipose tissue in the treatment of pain and function in patients with knee OA.

MATERIALS AND METHODS

1. Study design

The present study will be conducted from June 2020 to December 2021 at the Omnihospital, an affiliated center to the Universidad Católica de Santiago de Guayaquil Ecuador, and the support of the Instituto de Investigación e Innovación de Salud Integral, Medical Faculty of the same University and Maastricht University, The Netherlands. This will be a phase III trial, triple arm randomized open label dose to be conducted as a single intra-articular injection of MSC in 3 groups of patients with the diagnosis of knee OA grade II and III (Ahlbäck classification),²² one receiving BM-MSC other receiving AD-MSC and the other BM-MSC + AD-MSC.

2. Study population

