- v. Application of the WOMAC Questionnaire (Western Ontario and McMaster Universities Osteoarthritis Index)²³. The Index contains 24 questions five items for pain (score range 0–20), two for stiffness (score range 0–8), and 17 for functional limitation (score range 0–68). Individual question responses are assigned a score of between 0 (extreme) and 4 (None). Individual question scores are then summed to form a raw score ranging from 0 (worst) to 96 (best). Finally, raw scores are normalized by multiplying each score by 100/96. This produces a reported WOMAC Score of between 0 (worst) to 100 (best).
- vi. Pain measurement with the Visual Analogue Scale (VAS). Visual analogue scales (VAS) are psychometric measuring instruments designed to document the characteristics of disease-related symptom severity in individual patients and use this to achieve a rapid (statistically measurable and reproducible) classification of symptom severity and disease control.
 - a) Restriction of pain medication. Any NSAID 15 days before procedure; and 12 months after.
- vii. Extracellular Matrix (ECM) preparation 3 weeks prior to procedure. Infiltration with procaine 2% by repolarization of the cell membrane in order to improve ECM at the areas to work.

* Each patient from all groups will receive 2 injections of procaine before the procedure. On week 1 and 3.
- ix. No cortisone injections will be permitted before or even 3 months previous to the procedure.

b. Intra-operative:

- i. Independent of MSC source and in order to know the amount and types of injected MSCs, flow cytometry will be used processing of the cells immediately after extraction and prior to the injection into

the knee. In 2006, the International Society for Cellular Therapy proposed minimal phenotypic criteria for the definition of cultured MSCs: expression of CD73, CD90, and CD105, and lack of CD11b or CD14, CD19 or CD79, CD45, and HLA-DR expression²⁴. It should be noted that the main criteria for MSCs are (1) plastic adhesion; (2) the above described phenotype; and (3) their tri-lineage differentiation potential²⁴.

- ii. *CD90 FITC, CD73 PE, CD105 PerCP-Cy5.5* phenotypic expression are measured regarding quantity and viability for all groups of patients.
- iii. *CD34PE, CD11b PE, CD19 PE, CD45 PE, HLADR PE, lack of phenotypic expression, will be measured.*

c. Post-operative:

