- i. AD-MSC will be joined with BM-MSC in a same syringe for application of the percutaneous injection (AD MSC + BM MSC group) into the affected knee.

7. FOLLOW UP.

All patients will be evaluated measuring scores of the WOMAC (Western Ontario and McMaster Universities Osteoarthritis Index)²³ and the VAS (Visual Analogue Scale), before treatment and then at 1, 3, 6, 9 and 12 months.

STUDY FLOW CHART
MSC IN OA

Patient: _____

STUDY FLOW CHART	VISIT 1	VISIT 2	VISIT 3	VISIT 4	VISIT 5	VISIT 6	VISIT 7	VISIT 8	VISIT 9	VISIT 10
Protocol Concept Sheet	Week 1	Week 2	Week 3	Week 4	Week 6	Month 3	Month 6	Month 9	Month 12	Month 15
Diagnosis	X	X								
Orthopaedic exam	X									
X RAYS		X								
MRI T2 map		X								
Laboratory		X								
Inclusion/Exclusion		X								
Informed Consent		X								
Pre Op Evaluations		X								
VAS		X								
WOMAC		X								
Preparation	X		X							
Randomization				X						
Procedures					X					
BM MSC					X					
AD MSC					X					
Flow Citometry Order					X					
Post Op Evaluations					X					
Sticks removed					X					
VAS						X	X	X	X	
WOMAC						X	X	X	X	
MRI T2 map							X			
Adverse Event Evaluation					X	X	X	X	X	
Results										X

MD. Signature

Date.

[figure not shown]
Figure 2. Clinical Trial MSC/OA Protocol Sheet.

Statistical Analysis.

The sample size is determined using the tool of G*Power VERSION 3.0.10. The parameters are applied for the selected F test, two-way mixed ANOVA (repeated measures, with immediate interaction). Given that none of these approaches have been previously compared, either separately or combined, the calculation was conducted considering a medium effect size ($f=0.25$). We established an error probability α of 0.05 and power of 0.95. We calculated the application of 3 repeated measures, even though 6 measures will be conducted for some variables (i.e., the VAS or WOMAC questionnaire).

Based on this criteria, the sample size would be 54, meaning that each group will consist of 18 individuals. The information previously mentioned is represented in detail in the following table and illustrated in a graph below it.

F tests - ANOVA: Repeated measures, within-between interaction		
Analysis:	A priori: Compute required sample size	
Input:	Effect size f	= 0.25
	α err prob	= 0.05
	Power (1- β err prob)	= 0.95
	Number of groups	= 3
	Repetitions	= 3
	Corr among rep measures	= 0.5
	Nonsphericity correction ϵ	= 1
Output:	Noncentrality parameter λ	= 20.250000

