This study applies descriptive statistics for determining the frequency and proportions for demographic variables (age, gender, education, and ethnicity) and clinical states (severity of knee osteoarthritis, time with disease, comorbidities). Likewise, for calculating the mean and standard deviation of age, WOMAC scores (and each element of the scale) and VAS.

We utilize the two-way mixed ANOVA to compare the differences of means between treatment groups for each dependent variable (WOMAC scores, VAS, and radiological changes). With respect to the WOMAC scores, not only we will analyze the scores in general, but also each score value of the three different components separately (pain, stiffness, function). The tests will determine if there is an interaction between the dependent variable and the factors (independent variables). The factors will be the type of treatment (between subjects) and time (within subjects). For the type of treatment, it

is categorized into: BMSCS only, AD-MSc only, and BM-MSc and AD-MSc combined.

As for the time factor, this will differ according to the dependent variable held for analysis. For example, the analysis of WOMAC and EAV scores will be evaluated in 6 different periods of time. The patients will be asked to respond to our questionnaires three weeks before the intervention and 1, 3, 6, 9, and 12 months after intervention (surgery). With respect to radiological changes, the T2 mapping MRI will be performed twice before the procedure and again six months later.

To guarantee the reliability of the analysis, we will test the atypical values by utilizing box diagrams and the normality with the method of Shapiro-Wilk. Furthermore, the homogeneity of variations will be evaluated with inferential statistic Levene tests, while the homogeneity of covariances with multivariate statistical Box's M test. Consequently, to comply with the hypothesis sphericity, a Mauchly's test will be conducted. In the case of a violation of an assumption, different tests will be utilized.

Finally, in the case of a treatment complication, there will be mixed lineal models generalized for determining the probability of each intervention. The complications considered in this investigation are pain and hematomas in the surgical place where stem cells were extracted, knee pain, and synovial effusion.

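### The trial is sized and analysed on a non-directional group-by-time interaction, with no combination-versus-single-source pain contrast to decide H1

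*Combined protocol and SAP*

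**What the plan says.** The Hypothesis Testing section states a directional claim about pain: "H1: The combined use of BM-MSC and AD-MSC is superior for pain management in knee OA, than the use of BMSC or AD-MSC alone". Its H0 is wider, ending "solely from adipose tissue in the treatment of pain and function in patients with knee OA", so function enters the null but not the alternative. Main goals, item (a), sets a more general aim, to "compare three types of intra-articular injections of MSC populations obtained from two clinically relevant sources".

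The sample-size table under Statistical Analysis is headed "F tests - ANOVA: Repeated measures, within-between interaction", with f = 0.25, alpha 0.05, power 0.95, three groups, three repetitions and correlation 0.5, giving 54 patients (18 per arm). The analysis text applies a two-way mixed ANOVA "to compare the differences of means between treatment groups for each dependent variable (WOMAC scores, VAS, and radiological changes", and for WOMAC also "each score value of the three different components separately (pain, stiffness, function". Its purpose is given as: "The tests will determine if there is an interaction between the dependent variable and the factors (independent variables". Every test uses p<0.05.

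The Evaluations section lists "Pain measurement with the Visual Analogue Scale (VAS" as the pain measure, but neither VAS nor WOMAC pain is called primary. VAS and WOMAC are planned at six time points in the text, and none is named as decisive.

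**The concern.** An interaction F test across three groups asks whether the time profiles differ in any way. It does not ask whether the combination is better, or better than which arm. A significant result can arise with the combination best, worst, or no different from one of the single sources.

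The observed means will show a direction. The plan does not say which comparison, outcome or visit then settles H1. The trial is open label and offers two pain measures and five post-treatment time points, so a choice not made now can only be made with treatment and results in view. The wording of H1 adds a further choice: its 'or' does not say whether the combination must beat both single sources or only one.

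The 0.95 is correctly labelled as power for the interaction. A reader may still take it as the chance of confirming H1. That chance depends on a pattern of means that the plan does not state.

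**Working it through.** **1. Reproduce the plan's figure.** Inputs from the sample-size table: f = 0.25, N = 54, k = 3 groups, m = 3 measures, correlation ρ = 0.5, no sphericity correction.

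λ = f²·N·m/(1−ρ) = 0.0625 × 54 × 3 / 0.5 = 20.25, as printed. Degrees of freedom are (k−1)(m−1) = 4 and (N−k)(m−1) = 102. Critical F is 2.461 and power 0.958. N = 51 gives 0.946, so 54 is the smallest multiple of three that reaches 0.95. The arithmetic is right.

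**2. Which patterns give that power?** Assumed, not in the documents: SD 1, equal arms at baseline, and differences sustained after baseline. If one arm is displaced by δ, the sum of squared group deviations is 2δ²/3, and that of the time profile (0, 1, 1) is 2/3. So

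λ = 18 × δ² × (2/3) × (2/3) / 0.5 = 16δ².

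Setting this to 20.25 gives δ = 1.125 SD. Because δ is squared, and the formula is the same whichever arm moves, power is 0.958 for any single arm in either direction. For equally spaced arms with spacing s, λ = 18 × 2s² × (2/3) / 0.5 = 48s², so s = 0.65 SD gives the same 0.958.

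Other visit schedules, with one arm displaced 1.125 SD:
- Five occasions, as ticked in the flow chart: λ = 24.30, power 0.956.
- Six occasions, as in the text: λ = 25.31, power 0.950.
- Divergence growing linearly: 0.879 (three visits), 0.885 (five), 0.930 (six).

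**3. What would a rule that answers H1 show?** Simulated with 18 per arm and ρ = 0.5, at one post-baseline visit, with baseline as covariate and a common slope (50 df). 'Both' means each contrast is significant at two-sided 0.05 in favour of the combination. 'Either' means at least one is, after Holm.

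| True pattern (interaction f = 0.25 throughout) | Interaction | Both | Either |
|---|---|---|---|
| Combination 1.125 SD above two equal arms | 0.958 | 0.94 | 0.98 |
| Graded, combination ahead by 0.65 and 1.30 SD | 0.958 | 0.59 | 0.98 |
| Combination equals AD, BM lags by 1.125 SD | 0.958 | 0.025 | 0.94 |
| Combination equals BM, AD leads by 1.125 SD | 0.958 | 0.000 | 0.022 |
| Combination worst by 1.125 SD | 0.958 | 0.000 | 0.000 |

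The interaction test gives the same answer in every row. H1 is true in the first two rows on any reading, in the third only on the 'either' reading, and false in the last two.

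**4. Multiplicity on pain alone.** Reading VAS and WOMAC pain each at 0.05 gives a false-positive chance of at most 0.05 + 0.05 = 0.10, and 1 − 0.95² = 0.0975 if they were independent.

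**The case against.** The plan also says the ANOVA compares group means, and an omnibus test is a fair answer to goal (a). The first part does not rescue H1. The treatment main effect is likewise a three-group test without direction, and it was not the effect sized. The second part stands, and the interaction test should stay for that purpose. The unnamed alternative tests apply only when an assumption fails, so they do not supply the contrasts.

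The 'both' figures show only one reading of H1. On the 'either' reading, a significant interaction when the combination equals AD and BM lags is not misleading. This is fair, and the table gives both readings. The last two rows are false leads on either reading.

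The 0.94 and 0.59 rest on baseline adjustment, which the plan does not contain. An unadjusted change at one visit gives 0.85 and 0.48 for the same two patterns. Baseline adjustment is a recommendation for efficiency. Contrasts within the planned mixed model would also address H1.

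The documents do not say when the missing choices would be made. That is so, but a choice not written down cannot later be shown to have been made in advance.

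**Conclusion.** The concern holds. The plan states a directional hypothesis about pain and provides no test that decides it. This follows from the text alone: no directed contrast, primary pain outcome, deciding visit, both-or-either rule or multiplicity rule appears, and H0 and H1 do not match.

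The sample-size calculation is correct for what it names. At its own effect size the interaction is significant about 96% of the time whether the combination is best or worst. Success on a baseline-adjusted rule to beat both sources ranges from 94% to essentially zero over the patterns shown, and is 59% in a graded pattern where H1 is true. Those figures assume SD 1, correlation 0.5, no dropout and the stated patterns of means, none of which except the correlation is in the documents. The need for a decision rule does not depend on them.

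**What to change.** Before any outcome data are examined, amend the Statistical Analysis and Hypothesis Testing sections as follows.

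1. Name one primary pain outcome (VAS or WOMAC pain) and one visit or a time-averaged post-baseline value. The choice is the sponsor's.
2. Make combination minus BM and combination minus AD, adjusted for baseline, the primary contrasts.
3. State whether H1 means better than both (each contrast at two-sided 0.05, no alpha split) or better than either (Holm across the two), and align H0 with H1.
4. Keep the interaction test as supportive and as the answer to goal (a). Make other outcomes and visits secondary, reported with confidence intervals.
5. Report power for the chosen rule at N = 54, with the assumed means, beside the interaction power.

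The cost is wording and two contrasts on data already planned. Secondary outcomes could no longer support a positive claim alone. Power for H1, which the plan does not now state, may prove lower than 0.95. Power to beat both with 18 per arm, BM equal to AD and ρ = 0.5:

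| Analysis | 0.5 SD | 0.75 SD | 1.0 SD | 1.125 SD |
|---|---|---|---|---|
| Unadjusted change, one visit | 0.17 | 0.44 | 0.74 | 0.85 |
| Baseline-adjusted, one visit | 0.23 | 0.58 | 0.86 | 0.94 |
| Baseline-adjusted mean of five visits, sustained difference | 0.55 | 0.93 | 0.997 | >0.999 |
| Same, difference growing linearly to month 12 | 0.12 | 0.32 | 0.58 | 0.71 |

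Visit versus average is therefore a real trade-off. The five-visit mean includes month 1, which the text plans but the flow chart does not tick for VAS or WOMAC. Averaging months 3 to 12 only, the last figure becomes 0.86, so the trade-off shrinks but remains. If the sponsor wanted 95% power for the weaker contrast in the graded pattern (0.65 SD, or 0.65/√0.75 = 0.75 residual SD after adjustment), about 48 per arm would be needed. That is a separate decision, and the fix does not require it.

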A total of 54 patients with the diagnosis of knee OA grade II and III will be recruited to receive a single intra-articular injection of MSC: Group 1 (n 18 patients) will receive BM-MSC and Group 2 (n 18 patients) will receive AD-MSC, and Group 3 (n 18 patients) will receive BM-MSC + AD-MSC.

a. Inclusion criteria:

- i. Patients aged 18 to 70 years, with grade II and III knee OA, according to the Ahlbäck classification will be included. Identified by two different observers.
- ii. Minimal VAS pain score of 4.
- iii. Chronic knee pain of mechanical origin.
- iv. All patients who sign a specially prepared informed consent for this clinical trial.

b. Exclusion criteria:

- i. Varus or valgus knee mal alignment superior to 10°.
- ii. OA grade IV according Ahlbäck classification.
- iii. Bone marrow cancer like lymphoma.
- iv. Severe anemia.
- v. Active infections.
- vi. Pregnant patients.
- vii. Immune diseases such as Rheumatoid arthritis, gout or pseudogout arthritis, psoriasis.
- viii. Bone diseases such as Kahler and Paget.
- ix. Corticoesteroid and hyaluronic injections within the last 3 months.
- x. Knee surgery in the last 6 months.

3. Ethical considerations

- a. All patients will be informed of the study aims and have the choice to complete an informed consent.
- b. All patients will be informed about alternative treatments.
- c. This study will be approved by the Ethical Committee of Catholic University of Santiago de Guayaquil (UCSG).

4. Evaluations

a. Pre-Operative:

- i. Complete clinical and orthopedic evaluation.
- ii. Laboratory diagnostic tests (biometrics, coagulation parameters glycemia, and liver, pancreatic, renal and lipid profile).
- iii. Radiological exams: Knee X Rays with weight bearing.
- iv. Magnetic resonance of the knee with cartilage measurement. T2 Map. MRI T2 mapping of the cartilage is a non-invasive functional imaging technique delivering cartography of the T2 relaxation time of the cartilage without any contrast injection. It is sensitive to tissue anisotropy, and provides compositional information on the cartilage collagen network, water content and proteoglycans concentration.

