- i. Pain, function and quality of life will be assessed using VAS and WOMAC scales. All patients will be evaluated before treatment, and at 1, 3, 6, 9 and 12 months.
- ii. Magnetic resonance with T2 Map imaging will be performed at baseline to analyze cartilage damage and at 6 months control. This test allows the early diagnosis of areas of cartilage degeneration. In addition it evaluates the relaxation times of water, collagen and proteoglycans. Sequence to assess the structure of the cartilage²⁵.

5. Randomization.

A randomized non blind clinical trial with active control. For this purpose, the random number generator, found on the RANDOM.ORG ® website (available at <https://www.random.org/integers/>)²⁶ will be used to generate 31 random numbers. Value between 0 and 1. Format: 5 columns.

[figure not shown]

Figure 1: Study Design. W (week), M (month), V (visit), VAS (visual analogue scale), WOMAC (Western Ontario Mc Master University Osteoarthritis Index)

6. Procedures

a. **Stem cell obtaining procedures.**

All the procedures will be performed in the operating rooms of the Omnihospital by [name] and [name], both certified orthopedic surgeons. Both will know about the randomization in order to know the source from which MSCs will be obtained, in an ambulatory procedure under local anesthesia and sedation. Average procedure time to obtain de MSCs will be approximately 75 minutes.

b. **BM-MSc PROCEDURE. GROUP 1**

- i. Bone marrow aspiration will be performed using a standard surgical technique: fluoroscopically guided percutaneous puncture of posterior iliac crest bone.
- ii. A total of 60 ml of blood from bone marrow will be aspirated with a heparinized syringe.
- iii. Attach the heparinized syringe to a 150 um filter. Gentle push the bone marrow through the filter to another syringe.
- iv. Attach 45 degree dispensing tip to filtered bone marrow 60 cc syringe.
- v. Slowly transfer the BMA into the Neogenesis 60 cc kit concentrating device until you have reached the 60 cc mark. Secure the green cap and clear safety cap.
- vi. Centrifugation of Neogenesis 60 cc concentrating device. Match counterbalance for each concentrating devices +/- 1.0g. Spin at 4200 rpm / 2800 rcf for 10 minutes.
- vii. Place the concentrating device on the BPS (Benchtop processing station), secure the device with your right hand and slowly turn the knob with your left hand counterclockwise, until the bone marrow aspirate has reached the bottom of the luer slip fitting.

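### Ahlbäck grade (II or III) is known before randomisation but is used neither in the allocation nor in the efficacy models; the cost is precision and credibility, not bias of the randomised test

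*Combined protocol and SAP*

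**What the plan says.** Section 2.a (Inclusion criteria, item i) admits patients "with grade II and III knee OA, according to the Ahlbäck classification will be included. Identified by two different observers", and section 2.b excludes grade IV. In the study flow chart, X-rays and the eligibility check are at Visit 2 (Week 2) and randomisation is at Visit 4 (Week 4), so grade is on file before allocation.

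Section 5 (Randomization) opens with "A randomized non blind clinical trial with active control" and goes on to describe one list of random integers. It mentions no strata, blocks or minimisation.

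The Statistical Analysis section plans a two-way mixed ANOVA for VAS, WOMAC (total and three components) and T2 mapping. On its terms it says: "The factors will be the type of treatment (between subjects) and time (within subjects". No covariate is named. Severity appears only in the list of variables to be described: "clinical states (severity of knee osteoarthritis, time with disease, comorbidities".

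The sample size table is headed "F tests - ANOVA: Repeated measures, within-between interaction". The analysis text likewise says the tests look for an interaction, and the pre-treatment score is one of the six time points for VAS and WOMAC.

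**The concern.** The trial takes two severity grades, has two observers confirm them and sets an upper limit on severity, yet makes no inferential use of the grade it collects. With arms of 18, a list without strata will quite often leave the arms with visibly different grade mixes, and the stated model has no term that could account for this.

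At stake is how the comparison behind H1 (combination against each single source) will be read. If the combination arm happened to hold more grade II knees, readers would ask whether an advantage reflects the cells or the knees. In an open-label trial with no pre-specified adjustment, the only answer would be a post hoc one. If grade also predicts change after treatment, leaving it out of the model costs some precision whether or not the arms are balanced.

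**Working it through.** **1. The plan's own figure.** The inputs are in the Statistical Analysis section: "We established an error probability α of 0.05 and power of 0.95"; "the calculation was conducted considering a medium effect size", f = 0.25; 3 groups; 3 repetitions; correlation 0.5; nonsphericity correction 1.

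- λ = f² × N × m / (1 − ρ) = 0.0625 × 54 × 3 / 0.5 = 20.25, as printed.
- Degrees of freedom: (3 − 1)(3 − 1) = 4 and (54 − 3)(3 − 1) = 102. Critical F is 2.461 and power is 0.958.
- N = 51 gives 0.946, so 54 is the smallest multiple of 3 that reaches 0.95.

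The figure is reproduced, and nothing below changes N.

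**2. How often grade is unbalanced.** The documents do not state the grade III share, so K = 16, 27 or 38 of 54 is assumed. With exact arms of 18, the probability of a split (a, b, c) of the K grade III patients is C(18,a) C(18,b) C(18,c) / C(54,K). The gap is the larger of the differences between the combination arm and each single-source arm.

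| Grade III, of 54 | P(gap ≥ 5) | P(gap ≥ 6) |
|---|---|---|
| 16 | 0.18 | 0.08 |
| 27 | 0.24 | 0.12 |
| 38 | 0.18 | 0.08 |

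A gap of 5 is 5/18 = 28 percentage points. The median gap is 3.

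**3. Effect on a comparison of arm means or of a single visit.** The shift is (gap/18) × grade effect. For a gap of 5 and an assumed grade effect of 0.25–0.8 SD, it is 5/18 × 0.25 = 0.07 SD to 5/18 × 0.8 = 0.22 SD. The standard error of a two-arm difference is √(2/18) = 0.33 SD.

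**4. Effect on the planned interaction test.** The test uses within-patient contrasts over time. A grade effect that is the same at every visit, baseline included, drops out of those contrasts, and only a grade difference in change remains. This was simulated with 3 arms of 18, 3 time points, correlation 0.5 and half the patients grade III. The grade effect grew linearly from zero at baseline to the stated size at the last time point. There were 6,000 trials under the null and 4,000 under the effect that gives λ = 20.25. The adjusted model adds grade and grade-by-time.

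| Grade effect | Power, unadjusted | Power, adjusted | Type I, gap ≥ 5, unadjusted | Type I, gap ≥ 5, adjusted |
|---|---|---|---|---|
| None, or constant 0.8 SD | 95.7% | 95.3% | 4.3% | 4.5% |
| 0.5 SD on change | 94.8% | 95.3% | 5.2% | 4.5% |
| 0.8 SD on change | 93.2% | 95.3% | 6.8% | 4.5% |
| 1.2 SD on change | 89.6% | 95.3% | 8.3% | 4.5% |

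The gap in this table is the largest difference among all three arms; it was 5 or more in 29% of simulated trials. Over all trials, unadjusted type I error was 4.6–4.8% in every row. The type I columns rest on about 0.293 × 6,000 ≈ 1,760 trials, so their simulation error is about 0.5–0.7 points.

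**The case against.** A reader might infer that any grade imbalance goes straight into the treatment comparison and biases it. The documents do not support that reading, for three reasons.

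- The trial is sized on, and the analysis text targets, the treatment-by-time interaction with the pre-treatment score as a time level. A constant grade difference cancels there, as the first row of the second table shows. The shifts in step 3 therefore belong to arm-mean or single-visit comparisons, or to a grade effect on change.
- Chance imbalance under valid randomisation is ordinary random error. Averaged over all randomisations the test keeps its level.
- No section says how far grade II against III predicts VAS, WOMAC or T2 change. Grade is used for eligibility, and its prognostic weight is an inference. Gaps of 5 or more are also the less common case.

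All three points stand, and they limit the concern without removing it. The analysis text also speaks of comparing mean differences between treatment groups, and H1 is a claim about one arm against the others. Such comparisons are exposed even to a constant grade effect. Nor do the documents give any reason to rule out that grade alters response over a year.

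A further objection is that the allocation list has a larger fault: 31 numbers valued 0 to 1 cannot assign 54 patients to three arms. That is a separate and more serious point. Because the list has to be rewritten anyway, stratifying it adds little work.

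**Conclusion.** The concern holds as a matter of precision and credibility. Grade is available two visits before randomisation, is absent from both the allocation and the models, and will differ by 5 or more of 18 between the combination arm and a single-source arm in roughly one trial in five (18–24%).

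For the planned interaction test, the cost is nil if the grade effect is constant. If grade changes response by an assumed 0.5–1.2 SD, it is about 0.5 to 6 points of power (95.3 − 94.8 = 0.5; 95.3 − 89.6 = 5.7). Type I error in the visibly unbalanced trials is then about 5–8% where adjustment gives about 4.5%.

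These sizes rest on an assumed grade share, an assumed grade effect, three time points as in the plan's own calculation, and arms of exactly 18. The documents fix neither the share nor the effect, so they cannot show that the loss is large. They do show that it is avoidable at little cost.

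**What to change.** - **Analysis.** State in the Statistical Analysis section that Ahlbäck grade (II/III, as fixed at Visit 2) and grade-by-time are terms in every efficacy model: VAS, WOMAC total and components, and T2. Name grade-by-time explicitly, because grade alone does nothing for the interaction test.
- **Allocation.** When the list is rewritten for three arms and 54 patients, generate it separately for grade II and grade III, in permuted blocks of varying size that are concealed from the site. Fixed blocks of three would make every third assignment predictable in a single-centre, open-label trial whose surgeons know the allocation.
- **Cost.** Two lists instead of one and one added sentence. The model spends one between-subject degree of freedom plus up to five within-subject ones (six time points for VAS and WOMAC; one for T2, with two time points). If grade is irrelevant, power falls by about 0.4 points (95.7% to 95.3%). Incomplete last blocks may leave arms slightly different from 18.
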